In the BCH CICU, approximately 10-15% of neonates undergoing a stage I palliation (S1P) experience PLOC and receive some resuscitation, often times in the form of extracorporeal membrane oxygen (EMCO) device support. These patients often experience increased ICU and hospital lengths of stay, higher hospital morbidity and mortality, and worse neurologic outcomes.⁴⁻⁶ The purpose of this study is to determine whether continuous monitoring of VO_2 and SVC saturations will allow development of signs to predict which patients are at highest likelihood of experiencing a PLOC before the event, permitting time for interventions to take place prior to an injurious or potentially lethal event.

[figure not shown]

Figure 2. In patients born with an inadequate left ventricle, the right ventricle is used to pump blood to both the body and the lungs simultaneously and in parallel by connecting the pulmonary artery to the small aorta, and creating a shunt from this circulation to the lungs. This circulation leads to increased oxygen demand for the heart. When this demand is not met, myocardial dysfunction and PLOC result. Figure from Ohye, *NEJM*, 2010. {Ohye:2010kn}

Currently Used Markers of Oxygen Delivery

Assessing the physiologic state of patients is a complex but vitally important task. At the bedside, the clinician combines many pieces of data to assess the adequacy of end organ oxygen delivery, each of which has strengths and weakness as a clinical sign. Basic hemodynamic parameters (aka vital signs) include a patient's heart rate, arterial and venous blood pressures, oxygen saturations and temperature are central to the assessment of a patient's physiologic state, and are often the most important clues to inadequate oxygen delivery. Further to this includes markers of end organ function, such as urine output, coagulation parameter, as well as laboratory indices of hepatic and renal function add some degree of confidence that our general assessments are correct.

In patients at higher risk of insufficient DO_2 , advanced monitoring techniques are commonly used. The three most commonly used techniques in routine use in neonates undergoing congenital heart surgery include (1) cerebral near infrared spectroscopy (cNIRS), (2) SVC saturation sampling, and (3) serum lactate measurements.

Cerebral NIRS

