exhibited a pronounced decrease in their measured VO_2 , a pattern which was not present in treated animals which did not experience subsequent hemodynamic instability (**Figure 3**). Having seen this pattern consistently in approximately $n=40$ animal experiments (weight range 2.5-4 kg), we hypothesize that in critically ill patients, VO_2 may decrease below the critical DO_2 and exhibit measureable, even striking, decreases prior to hemodynamic decompensation takes place. If this hypothesis is true, quantification of VO_2 may represent a new 'vital sign' which represents end organ oxygen delivery in critically ill patients. Identification of patients with pathologically supply dependent VO_2 may permit definitive interventions to take place, e.g. initiation of extracorporeal life support, prior to a life-threatening PLOC.

Study Objectives

Specific Aim 1. To demonstrate that oxygen consumption (VO_2) and superior vena cava (SVC) saturations can be safely and precisely measured continuously in newborns undergoing surgery for hypoplastic left heart syndrome (HLHS) or d-transposition of the great arteries with an intact ventricular septum (d-TGA/IVS).

Hypothesis: Measurement of these oxygen-based parameters will not be associated with an increased incidence of equipment-related adverse events (e.g. line displacements, inadvertent extubations) and will lead to precise and reproducible measurements of these important parameters.

Specific Aim 2. To determine whether postoperative loss of circulation (PLOC, defined as cardiac arrest requiring CPR, ECMO cannulation, or causing death) in these patients are associated with a change in oxygen consumption or SVC saturation prior to the event.

Hypothesis: PLOC will be associated with significant decreases in both oxygen consumption and SVC saturations for at least 10 minutes prior to the onset of cardiac arrest.

Specific Aim 3. To determine whether the addition of the oxygen-based measurements to standardly measured parameters (i.e. vital signs, near-infrared spectroscopy

[figure not shown]

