In lieu of the standard Cook Medical catheter, the treating team will place a similar FDA-approved catheter, but which is fitted with a fiberoptic sensor which continuously records the oxyhemoglobin saturation of the blood to which it is exposed. The catheter is 4.5 French, 5 cm in length, has two lumens, and is Heparin bonded (PediaSat catheter, Edwards LifeSciences, Model# XT245HK, see **Figure 5**). The catheter comes with a sterile percutaneous insertion kit. As above, all cardiac intensivists, cardiac anesthesiologists and CICU nursing staff will receive a formal training on the insertion and care of this catheter by the company representative ([name]). Prior to insertion, the catheter will be calibrated using an in vitro solution which comes with the catheter. For those familiar with the device, this process will add 2-3 minutes to the insertion time. Following insertion of the catheter, the device will be attached to the study monitor (Datex Ohmeda Critical Care Monitor, GE Healthcare) via a specialized cable. The catheters will be paid for by the PI.

Figure 5. The PediaSat catheter to be used in this study is functionally the same as catheters routinely used in the perioperative care of newborns with CHD except that it is fitted with a fiberoptic probe at its tip which continuously reads SVC saturation.

In the opinion of the study team, the SVC saturation is a clinically useful piece of data which is routinely used at BCH in the management of patients. Because the device readings have been shown to correlate well with oximetric readings from venous blood, the SVC saturation will be continuously displayed on the study monitor for clinicians to use at their discretion for the duration of the study.

The study will end following the first postoperative extubation or removal of the central venous catheter, whichever occurs last.

Endpoints/Outcomes

Primary Outcome. The primary outcome being measured will be a composite endpoint of PLOC, including the need for CPR, the need for ECMO in the setting of CPR, or death.

Secondary Outcomes. Because Aim 3 of this study is to determine whether the aforementioned oxygen-based measurements add to the predictive power of the data standardly used to assess patients, there will be a substantial amount of data gathered, which is outlined below.

- Oxygen-based parameters unique to this study

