Quality in the data collected by the oxygen consumption monitor will be ensured by a self-test at startup according to the manufacturer's instructions. Further, anesthesiologist and respiratory care staff will be instructed to monitor for the degree of air leak from the respiratory system by calculating the difference between inspiratory and expiratory measured tidal volumes. If the airleak exceeds this value, air may be added to the tracheal tube cuff. We have shown that when this difference is <15%, VO_2 data are accurately measured in newborns.²⁴ Further, an absence of end-tidal CO_2 data will be used as a signal of an endotracheal tube disconnection and possible suctioning event. VO_2 measurements are known to be unstable for several minutes following suctioning²⁸, so we will exclude VO_2 data for 10 minutes following any ETT disconnect from analyses.

Figure 6. The oxygen-based monitoring and data collection systems utilized for this study are attached to a rolling pole which can be placed anywhere around the patient and easily moved for convenience and safety.

Data within the SVC monitoring probe will be ensured by an in vitro calibration prior to probe insertion. When ever the treating team sends a venous blood gas from the central venous line, the co-oximetry value will be entered into the machine and used to recalibrate the probe in real-time.

Quality in the transfer of data from the medical record to the spreadsheet will be ensured by an independent review of the primary data by a second member of the study team. Furthermore, when possible, the fields for data entry will contain 'Data Validation' functions (i.e. value will turn red if outside expected limits, and hard stops will be inserted for physiologically impossible values). Additionally, drop down lists will be utilized when possible to minimize data entry errors.

Data Analysis Plan

Patients will be divided into patients who do and do not experience PLOC. All variables will be normalized to hours prior to bypass, bypass time and hours post-bypass time, such that all data for a specific post-bypass time will be aligned between patients. All weight-dependent variables will be normalized to preoperative body weight. Using GraphPad Prism, each variable will be entered into a different column for analysis.

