Simple analyses (e.g. mean, standard deviation, tests for normality) will be completed within GraphPad. With regards to the primary endpoint, VO₂ measurements will be analyzed for 120 minutes prior to a PLOC event in cases, and a randomly selected 120 minute period in controls. Values will be compared between cases and controls using generalized estimating equations (GEEs) to account for the correlation of multiple measurements within the same patient and to compare means between cases and controls. A post-hoc broken stick analysis will be used to determine the time prior to the event at which the VO₂ changed in each patient experiencing an event. Data for HLHS and dTGA patients will be pooled together.

More complex analyses will be completed by a collaborating company called Etiometry (including [name] and [name], co-investigators on this study), with whom the PI and others within the CICU have an established relationship. Deidentified information will be sent to the company, who will complete further analyses.

Power Calculations and Sample Size

The measured oxygen consumption in neonates following S1P has been described as 86 ± 16 mL/min/m^{2.22}. A sample size that includes 3 cardiac arrest events would allow us to detect a true decrease of 53 mL/min/m² in oxygen consumption with 90% power and a significance level of 0.05 (two tailed). Based on the significant change in VO₂ noted in the animal studies preceding cardiac arrest, we do not feel that this number is an unreasonable number. In order to collect 3 patients meeting the endpoint, we predict that we will require 20 patients undergoing S1P.

Risks and Discomforts

Because this is a prospective, observational study which we do not expect to change the standard of care, the risks associated with this study are really those of the standard

of care. The VO_2 measurements will be taken using an FDA-approved device which samples gas from the side of the tracheal tube of each patient. In reality, the adapter used by the study monitor is smaller and lighter than than used in our current capnographs, so the risk of accidental endotracheal tube removal should be the same or lower.

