- *Earlier recognition of circulatory failure.* Regardless of a patient's underlying anatomy, the difference in oxyhemoglobin saturation between a patient's systemic arterial and venous circulations represents the adequacy of end organ oxygen delivery (reference Figure 1 above). It is possible that by continuously monitoring both the systemic arterial and venous oxyhemoglobin saturations (the former by pulse oximetry), that the treating team will be able to more rapidly identify evolving circulatory failure. There are many interventions which could be utilized

by the care team prior to PLOC which may improve patient outcomes as a result of and in response to this single factor.

Potential Indirect Benefits

This study has the potential to significantly improve the way that newborn patients (and others) are monitored in the postoperative period. Currently, the circulation of these patients are assessed indirectly, using surrogate measures (using cNIRS, and intermittent lactate and SVC saturations measurements) and vital signs. Because our definitive treatment for refractory circulatory failure is ECMO, and because ECMO itself can cause life-threatening complications, it is extremely challenging to determine which patients are at a higher risk of death or organ injury from inadequate DO_2 compared to the risks of these complications from ECMO. It is possible that if the primary hypothesis of the study, that critically ill patients in the CICU exhibit pathologically supply dependent oxygen consumption, that VO_2 monitoring could add significant, continuous, noninvasive information to the care of newborns during their highest risk period. For the short term, this could permit treating teams to measure the effects of their interventions on oxygen delivery (e.g. addition of inotropes, blood transfusions, clips on shunts) and inform these decisions. For the long-term, it is possible that VO_2 and continuous SVC saturation monitoring could inform a predictive algorithm for the sensitive and specific prediction of which patients suffer from recalcitrant circulatory insufficiency, those which may be at risk for PLOC, and who would benefit from ECMO support. If true, this would likely significantly improve the survival rate and neurologic outcomes of newborns with congenital heart disease.

Privacy and Confidentiality Provisions

Privacy Provisions

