Appendix 1. Study schematic

Appendix 2. Parent informational flyer

Oxy-CAHN Study

Oxygen consumption-based assessments of hemodynamics in neonates following congenital heart surgery

Enrollment Criteria

Preoperative HLHS (n = 20)
OR
d-TGA/IVS (n=20)

Assent of cardiac surgeon and cardiac intensivist
Parental consent

Cardiac OR

At first intubation*

- > Calibrate VO_2
- > Check ETT leak
- > Begin data collection

At CVL insertion*

- > In vitro calibration
- > Catheter insertion
- > Confirm position in SVC

Cardiac ICU

Daily collect:

- > Primary outcome (CPR, ECMO, death)
- > VO_2 and SVC saturations
- > Cardiac output and Q_p/Q_s
- > NIRS, lactate, UOP
- > Inotropes
- > Blood loss and transfusion
- > Sedatives, paralytics
- > Feedings
- > Vital signs

From S5 Collect™

From medical record
and discussion with
primary team

From T3 database

* Enrollment begins at either first intubation or central venous line insertion (whichever occurs first) and ends at first postoperative extubation or central venous line removal (whichever occurs last).

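### The primary outcome counts ECMO only with CPR in one place and without condition in another, so a survivor given ECMO without CPR can be a case or a control

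*Combined protocol and SAP*

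**What the plan says.** The definition of PLOC appears in three places in the combined protocol and SAP.

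- Endpoints/Outcomes, Primary Outcome: a composite "including the need for CPR, the need for ECMO in the setting of CPR, or death".
- Study schematic (Appendix 1), among the items to collect daily: "Primary outcome (CPR, ECMO, death", with no condition on ECMO.
- Study Objectives, Specific Aim 2: "defined as cardiac arrest requiring CPR, ECMO cannulation, or causing death". The Aim 2 hypothesis times the change in oxygen consumption (VO2) "for at least 10 minutes prior to the onset of cardiac arrest".

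Power Calculations and Sample Size counts arrests: "A sample size that includes 3 cardiac arrest events". The background section on HLHS gives the rate: "approximately 10-15% of neonates undergoing a stage I palliation (S1P) experience PLOC".

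On use of the definition, the Data Analysis Plan states: "Patients will be divided into patients who do and do not experience PLOC". It pools the HLHS and d-TGA infants. VO2 is analysed over the 120 minutes before the PLOC event in cases and over a 120-minute window drawn at random in controls. No limit is set on where the control window may fall.

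Two exclusions bear on this. Preoperative ECMO is an exclusion criterion, and VO2 is dropped for 10 minutes after a tube disconnection (Quality control methods). No text stops recording when ECMO starts.

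**The concern.** In the Primary Outcome wording the ECMO component adds no infant, because anyone given ECMO in the setting of CPR already counts through CPR. In the schematic, ECMO is a component in its own right. The two wordings disagree about one kind of infant: a survivor given ECMO without CPR. Death counts everywhere, so non-survivors are not affected.

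The plan foresees such infants. Preliminary Studies names extracorporeal support as something that might be started before a PLOC, and Potential Indirect Benefits states that "our definitive treatment for refractory circulatory failure is ECMO". How often this happens without CPR is not given.

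Two things are at stake. First, the case group is very small, and one member's status depends on which text is followed, a choice that could be made after the data are seen. Second, if the infant is a control, its random window may cover time on ECMO. The background describes VO2 as measured from inspired and expired gas. Oxygen added outside the lungs would not be seen at the airway, so such a window would probably understate total uptake and pull the control mean towards the case mean. That is an inference; the documents do not say what the device reads on ECMO.

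**Working it through.** **Classification of a survivor given ECMO without CPR**

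| Text | Status |
|---|---|
| Primary Outcome section | Control |
| Study schematic | Case, time zero not stated |
| Aim 2 definition | Most naturally a control, since ECMO is tied to cardiac arrest |
| Sample size paragraph | Counts cardiac arrests, so consistent with control |

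**Inputs.** SD 16 mL/min/m², planned difference 53, mean 86, two-sided 0.05 and 3 events (Power Calculations and Sample Size). PLOC rate 10–15% after S1P (background). Pooled total 20 + 20 = 40 infants (Study Design; Data Analysis Plan).

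**The plan's own figure.** The plan states 90% power to detect 53 with 3 events. A two-sample t-test with SD 16 gives 85.3% for 3 v 3, 99.9% for 3 v 17 and 99.97% for 3 v 37. None is 90%, and the comparison behind the stated figure is not given. The present point does not depend on it.

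**Share of the case group.** Expected events are 20 × 0.10 = 2 to 20 × 0.15 = 3. Adding one ECMO-only infant makes it 1 of 3 or 1 of 4.

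**Infant as a control, window on ECMO.** Suppose its window reads L lower than other controls. The control mean falls by L / (number of controls). L is assumed to be 53 (as low as a case) or 86 (VO2 near zero, an upper bound). Arrest cases are 53 lower. Power is simulated with a simple t-test that ignores the GEE structure.

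| Arrest cases v controls | L | Shift in control mean | Power at 53 |
|---|---|---|---|
| 3 v 37 | 0 | 0 | 99.97% |
| 3 v 37 | 53 | 53/37 = 1.4 | above 99% |
| 3 v 37 | 86 | 86/37 = 2.3 | 99.4% |
| 2 v 38 | 0 | 0 | 99.4% |
| 2 v 38 | 53 | 53/38 = 1.4 | 98% |
| 2 v 38 | 86 | 86/38 = 2.3 | 95% |

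**Infant as a case.** Suppose its own drop before cannulation is e, assumed to lie between 0 and 53. With k arrests the expected difference is (53k + e)/(k + 1).

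- 3 arrests plus this infant (4 v 36): at e = 0, (3 × 53)/4 = 39.75, a fall of 13.25; at e = 53 there is no fall. Power at e = 0 is 99.2%.
- 2 arrests plus this infant (3 v 37): at e = 0, (2 × 53)/3 = 35.3, a fall of 17.7; at e = 53 there is no fall. Power at e = 0 is 92.5%.

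**The case against.** The best reply is that the plan largely settles the matter. The Primary Outcome section is where the endpoint is defined. The schematic is a list of items to collect, and its parenthesis may be shorthand. Aim 2 and the sample size paragraph both point to arrest. Preliminary Studies treats extracorporeal support as something that comes before PLOC, not as PLOC itself. On that reading the infant is a control, and the onset of arrest serves as time zero for every case.

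Most of this stands. A reader might infer that the primary outcome is undefined, or that cases in general lack a time zero. The documents do not support either: the weight of the text is on arrest, and time zero is missing only for an ECMO-only case, which exists only under the schematic's wording. But no text says which wording governs, and the schematic is where the primary outcome appears as a daily collection item. The arrest-based reading also leaves the ECMO-only survivor as a control with an unrestricted window.

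A second reply is that harm through the control window needs several things at once: ECMO without CPR, survival, VO2 still being recorded, and the random window landing on ECMO. That is fair. The calculation takes all of these as given, so the control-side shifts describe what happens if they occur, not what is expected on average.

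**Conclusion.** The point holds as a conflict between two current statements of the primary outcome, with a control-window rule that can admit time on ECMO. Severity is minor to moderate.

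Its weight comes from the small case group. Which wording is followed decides whether one infant joins a group of 2 or 3 arrests, and under the assumed range this lowers the expected difference by 0 to 13 (4 v 36) or 0 to 18 mL/min/m² (3 v 37). The control-side effect is small, 1.4 to 2.3 mL/min/m².

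A reader might infer that the study loses its power. It does not: power stays at about 95% or more on the control side and about 92% or more on the case side. A comparison confined to 20 infants would look worse (about 75% for 2 v 18 with one control reading 86 lower), but the Data Analysis Plan pools both diagnoses, so 40 is the right base.

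These figures rest on one such infant occurring, SD 16 for all infants, arrest cases 53 lower, a simple t-test in place of the GEE, and the assumed readings. The frequency of ECMO without CPR and the VO2 reading on ECMO are not in the documents.

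**What to change.** Before analysis:

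1. Reconcile Specific Aim 2, the Primary Outcome section and the schematic to one PLOC definition, and state time zero for each component.
2. If ECMO without CPR is not an event, keep those infants as controls but draw no control window after cannulation.
3. In that case, report one sensitivity analysis that counts ECMO without CPR as an event with time zero at cannulation. This also covers something the window rule alone does not: VO2 may already be low in the hours before cannulation, and a control window could still fall there.

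The cost is a wording amendment and one extra analysis. No new data are needed, since ECMO is already on the daily collection list. The downsides are slightly less eligible control time and a sensitivity analysis that will be empty if no such infant occurs.

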Cellular function and survival requires a continuous supply of oxygen to perform aerobic respiration. Inspired oxygen gas traverses pulmonary capillaries and binds to hemoglobin, which carries large amounts of the molecule to the systemic tissues. Systemic oxygen delivery (DO_2) is amount of oxygen carried by a given volume of blood multiplied by its flow rate (cardiac output). This represents the amount of oxygen available for tissues to consume. In healthy individuals, this supply exceeds demand by a substantial margin - some 60-70% of oxygen delivered to the tissues returns to the systemic veins unused. The volume of oxygen actually consumed by the tissues (VO_2) of course can never exceed DO_2 , and is generally governed by a patient's metabolic rate. In critically ill patients, factors which are known to increase VO_2 include fevers, seizures, activity and inotrope administration to name a few. In patients who are very critically ill, DO_2 may actually decrease below a critical threshold known as 'critical DO_2 ' (**Figure 1**).¹ Below critical DO_2 , the body's normal compensatory mechanisms (e.g. to increase cardiac output or increase the oxygen extraction ratio) are overcome, and an insufficient volume of oxygen is delivered to tissues, which in turn decreases VO_2 (since tissues cannot consume oxygen if it is not delivered).

[figure not shown]

Figure 1. Oxygen delivery is the amount of oxygen carried to the tissues, and typically far exceeds that which is needed/consumed by the tissues. As oxygen delivery decreases progressively (moving right to left across the X axis), a critical threshold is reached below which oxygen consumption decreases as tissues become dysoxic (A). As tissues become progressively hypoxic, an increasing amount of oxygen is extracted from hemoglobin, increasing the oxygen extraction ratio. Figure from Schumacker, *Int Care Med*, 1987.

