 - Oxygen consumption (Q1 second). The VO_2 will be recorded Q1 second as part of the ventilatory parameters described below.
 - SVC saturations (Q1 second). SVC saturations as determined by oximetry will be recorded Q1 second.
- Standard of care monitoring
 - Vital signs. These data will include heart rate, arterial blood pressures, respiratory rate, pulse oximetry, atrial pressures, and central venous pressure. As discussed in detail below, these data will be extracted from an existing program which records the primary data Q5 second in time stamped fashion (T3 Program, Arcardia Solutions).
 - *NIRS*. The near-infrared spectroscopy value represents the oxyhemoglobin saturation of the deep tissues. This will be recorded Q1 second in time-stamped fashion.
 - *Ventilatory parameters*. All ventilation parameters will be recorded from the spirometry recordings from the capnograph. These data include end-tidal CO_2 , fraction of inspired CO_2 , respiratory rate, fraction of inspired O_2 , fraction of expired O_2 , peak end expiratory pressure, peak inspiratory pressure, plateau pressure, mean airway pressure, airway resistance, inspiratory-expiratory time ratio, inspiratory and expiratory times, inspiratory and expiratory tidal volume, compliance of the respiratory system, minute ventilation, VCO_2 , energy expenditure, and respiratory quotient. These data will be recorded Q1 second in time-stamped fashion.
- *Standard labs* will be drawn at the treating team's discretion and gathered from the medical record each day.
 - Arterial blood gas and time drawn
 - Serum lactate and time drawn
 - SVC (or other venous) saturations and time drawn
 - Chemistry profile, complete blood count (white blood cell count, hemoglobin, hematocrit and platelet count), coagulation profile and times drawn
- Treatments
 - *Inotrope infusions* are routinely administered, often in high doses, to these patients in the perioperative setting. It is thought that these infusions affect both oxygen delivery to all tissues, as well as increasing myocardial oxygen consumption.
 - Additionally, we will record *intermittently administered medications*, such as epinephrine, calcium gluconate, sodium bicarbonate, hydrocortisone, and

- thyroid replacement therapy, all of which may affect oxygen consumption and oxygen delivery as well.

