- Chest explorations and operative interventions performed at the bedside (e.g. clipping of BTS or Sano shunt) will be recorded each day from a review of the medical record, discussion with the primary team (including the bedside nurse) and the notes within the medical record.
 - Blood loss from chest tubes (in mL/kg each hour) and blood product administrations (including the blood products given and the times at which they are given) will be recorded from the medical record each day.
 - Sedatives and paralytics are routinely used and also affect oxygen consumption.
 - Diuretic medications are also routinely used, can affect preload.
 - Arrhythmias and
 - Other clinical parameters
 - Urine output is a crude marker of intravascular volume and end organ oxygen delivery.
 - The presence of enteral feedings, the rate of feedings and the caloric densities will also be recorded, as these may affect a patient's systemic vascular resistance.
 - Operative characteristics
 - Full preoperative and postoperative anatomic diagnoses
 - Residual anatomic defects
 - Total pump time, cross-clamp time, circulatory arrest time, regional perfusion time, minutes of continuous and modified ultrafiltration, blood products administered on bypass

Data Collection Methods, Assessments and Schedule

Outcome measurements

The majority of the endpoints presented above are routinely collected within the medical record as a part of patient care. Therefore, the majority of the data will be abstracted directly from the medical record and into a spreadsheet for data analysis by a member of the study team during each day for the duration of the study. The PI employs two full-time technicians within his lab who will assist with this labor intensive process.

- The oxygen-based measurements which are central to this study, including VO_2 , SVC saturation, as well as all ventilatory parameters listed above will be saved to a computer program (S5 Collect, GE Healthcare) attached to the patient's monitor. This program saves data in time stamped fashion Q1 second.
- Time-stamped vital sign data listed above will be exported daily from the hospital's in situ T3 program (Arcadia Solutions).
- The labs, treatments and other clinical parameters (see previous section) will be extracted in time-stamped fashion from the medical record each day by a member of the study team.

Patient variables

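### Temperature is not among the vital signs listed for extraction, and the VO2 case-control comparison takes no account of temperature or neuromuscular blockade, so a difference in metabolic demand could be read as inadequate oxygen delivery, or could mask it.

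*Combined protocol and SAP*

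**What the plan says.** **Temperature and VO2.** Background, The Importance of Oxygen Delivery, says that VO2 "is generally governed by a patient's metabolic rate" and, of critically ill patients, that "factors which are known to increase VO_2 include fevers, seizures, activity and inotrope administration to name a few". Background, Currently Used Markers of Oxygen Delivery, treats temperature as one of the basic vital signs: "heart rate, arterial and venous blood pressures, oxygen saturations and temperature are central to the assessment of a patient's physiologic state".

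**Data to be collected.** Under Endpoints/Outcomes, Secondary Outcomes, the vital-signs item reads: "These data will include heart rate, arterial blood pressures, respiratory rate, pulse oximetry, atrial pressures, and central venous pressure". Data Collection Methods then refers back to that list for the daily export from the T3 system. Temperature does not appear among the ventilatory, laboratory, treatment, clinical, operative or enrolment items either. The Appendix 1 schematic says only that vital signs come from T3.

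**Blockade and sedation.** These are listed for recording, under Treatments and again in Appendix 1. The protocol gives the reason: "Sedatives and paralytics are routinely used and also affect oxygen consumption".

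**Analysis.** The Data Analysis Plan takes VO2 over the 120 minutes before PLOC in cases and over a 120-minute window drawn at random in controls. It compares means by generalized estimating equations (GEE), pooling the two diagnoses. A post-hoc broken-stick analysis then looks for the time of change in each case. No covariate, matching or restriction is named. The one stated time-based VO2 exclusion, under Quality control methods, is the 10 minutes after a tube disconnection.

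**The concern.** The study's interpretive claim is that low or falling VO2 marks oxygen delivery below the critical level. By the protocol's own physiology, VO2 can also be lower because the tissues need less oxygen. Temperature and muscle activity are two routes to that, and the protocol recognises both.

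The control window is random, so nothing makes it resemble the case window in temperature or blockade status. If the groups differ on these, the GEE contrast mixes a demand difference with any delivery effect. The broken-stick step is exposed in a narrower way: a paralytic started, or a temperature change, inside the 120 minutes could itself produce the breakpoint.

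Followed as written, the plan provides no temperature series against which to check such a finding. The reverse error is also possible. Fever or inotropes in cases would raise VO2 and could hide a real fall.

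**Working it through.** **1. Where each item stands**

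| Item | Protocol says it affects VO2 | Listed for collection | Used in the VO2 comparison |
|---|---|---|---|
| Temperature (fever) | Yes, Background | No | No |
| Sedatives, paralytics | Yes, Treatments | Yes | No |
| Inotropes | Yes, Background | Yes | No |
| SVC saturation | Falls when delivery is inadequate, Background | Yes, every second | No joint reading with VO2 |

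Temperature has a gap in both data and analysis. Blockade has a gap in analysis only.

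**2. The plan's own figure**

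Power Calculations and Sample Size gives a mean of 86, an SD of 16, 3 events, 90% power, two-sided 0.05 and a detectable fall of 53 mL/min/m². This is reproduced by 3 cases against 3 controls, with a t critical value on 4 df and a normal quantile for power:

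(2.776 + 1.282) × 16 × √(1/3 + 1/3) = 4.058 × 13.06 = 53.0.

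The figure is not disputed here. It serves as the yardstick.

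**3. How large a demand shift could be**

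The documents give no size, so these are assumptions. Suppose demand alone lowers mean VO2 in cases by a stated share of 86, with delivery unchanged. Treat each patient as one mean with SD 16, and use the exact noncentral t. The entries on the right are the chance of a significant lower-VO2 finding; the nominal rate in that direction is 2.5%. Control numbers are 3 (which reproduces the plan's figure), 17 (20 stage I patients less 3 cases) and 37 (all 40 pooled, less 3).

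| Assumed fall | mL/min/m² | Share of 53 | 3 v 3 | 17 v 3 | 37 v 3 |
|---|---|---|---|---|---|
| 5% | 4.3 | 8% | 4.5% | 6.0% | 6.4% |
| 10% | 8.6 | 16% | 7.5% | 12.6% | 13.9% |
| 20% | 17.2 | 32% | 17.5% | 36.9% | 41.5% |
| 30% | 25.8 | 49% | 32.9% | 68.3% | 74.5% |

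**4. Temperature alone, as a second illustration**

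Assume VO2 changes 7% to 10% per °C and cases are 1 to 2 °C cooler. Neither range is in the documents.

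- 7%, 1 °C: 86 × (1 − 0.93) = 6.0
- 7%, 2 °C: 86 × (1 − 0.93²) = 11.6
- 10%, 1 °C: 86 × (1 − 0.90) = 8.6
- 10%, 2 °C: 86 × (1 − 0.90²) = 16.3

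The range of 6.0 to 16.3 is 0.4 to 1.0 of the SD (6.0/16 to 16.3/16) and 11% to 31% of 53 (6.0/53 to 16.3/53). If cases were warmer, the sign would reverse.

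**5. What SVC saturation adds**

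Background says inadequate delivery raises extraction and lowers venous saturation. A fall in demand with unchanged delivery should not lower it. The two explanations therefore predict different SVC behaviour. The Aim 2 hypothesis expects both VO2 and SVC saturation to fall, but the Data Analysis Plan describes the primary comparison for VO2 only.

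**The case against.** Several points on the other side are sound.

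- **The list may not be exhaustive.** It says what the data will include, Appendix 1 names vital signs without limit, and temperature may well sit in T3 or the chart. A reader might infer that temperature will not be captured at all. The documents support only that it is not listed. The remedy is still to name it, because the T3 export is tied to the list and Confidentiality Provisions has the identifier links destroyed after analysis. A value not extracted by then may be unrecoverable.
- **Demand and delivery are not inseparable.** A reader might infer that without temperature they can never be told apart. Continuous SVC saturation, lactate and time-stamped drug records partly separate them. What stands is that no joint reading is planned.
- **The broken-stick step is partly protected.** Stable blockade or stable cooling over the window produces no breakpoint. Only a change within the window does.
- **Direction is not established.** It is tempting to say that the sickest infants are cooler and more often paralysed, so that bias favours the hypothesis. No passage says so, and the factors named in Background raise VO2. Inotropes, often given in high doses according to Treatments, could push the other way.
- **Aims 2 and 3 are worded as association and prediction.** These do not need a causal reading. The claim that VO2 marks inadequate delivery, which the protocol calls central, does.
- **Adjustment is hard with about 3 events.** Time-varying covariates would be barely estimable. If low output itself changes temperature, adjusting could remove real signal. This limits the remedy; it does not remove the gap.

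**Conclusion.** The point holds as a gap in the listed data and in the specified analysis. The protocol recognises temperature and blockade as influences on VO2, does not list the first for extraction, and uses neither in the VO2 comparison. A demand difference could then be read as failing delivery, or could mask it.

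The size is conditional. Under the assumed temperature effect the shift would be well short of the planned 53 and could not by itself supply it. It need not be that large to mislead: an assumed 10% demand-driven fall would raise the chance of a false lower-VO2 result from 2.5% to between 7.5% and 13.9%, depending on the number of controls. That rests on 3 cases, one mean per patient, SD 16 and the assumed fall itself. The documents fix neither the sign nor the amount of any imbalance, so no claim of bias towards the hypothesis is warranted. The change is worth making because it is cheap and protects the interpretation of the main result.

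**What to change.** 1. Add time-stamped core temperature, from T3 or the chart, to the vital-signs list under Secondary Outcomes, so that the daily export covers it.
2. Keep the planned unadjusted GEE as the main VO2 comparison.
3. Add a pre-specified sensitivity analysis in which control windows are restricted or matched to the case's blockade status and to a similar temperature. Do not rely on time-varying covariate adjustment with about 3 events.
4. For each case, report temperature, blockade and sedation timing, and SVC saturation over the 120 minutes, beside the VO2 trace and the broken-stick breakpoint.
5. State the reading rule in advance: a VO2 fall is attributed to reduced delivery only if no concurrent change in temperature or blockade explains it and SVC saturation also falls.

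The cost is one extra field from an existing record, fewer eligible control windows and a somewhat wider interval in the sensitivity analysis. Enrolment, treatment and sample size are unchanged.
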